**Primary Objective:**

To assess the efficacy of rTMS in improving executive functioning in Veterans with mild to moderate TBI in order to maximize rehabilitation outcomes.

**Secondary Hypotheses:**

1. Sustained Improvement. At the end of the 6-month post treatment follow-up, TBI patients who received rTMS would be more likely to continue to have reduced symptoms, i.e. greater "executive function improvement" than patients who received sham rTMS.
2. Secondary consequences of TBI will improve with rTMS treatment, i.e. scores on Quality of Life (QOL) scale will show significantly greater improvement in patients with mild to moderate TBI who received rTMS treatment.
3. Moderators of Response. Age, severity of symptoms at baseline, type of comorbidity (PTSD, time since injury, sleep, depression substance abuse, medication use, cognitive exercises, fatigue or any combinations of these), TBI type, duration of

**Title :** Repetitive Transcranial Magnetic Stimulation to Improve Cognitive Function in TBI  
**Approval Period:** 12/11/2018 - 02/13/2019

illness and prior treatment resistance (rTMS/ECT): may affect or "moderate" treatment response.

4. Greater functional connectivity will be observed in hub centers of the Default Mode Network (DMN), particularly the precuneus/posterior cingulate area as measured by resting state fMRI at follow-up compared to baseline in those TBI patients treated with rTMS compared to those treated with sham.

5. Mediators of Response to Treatment: to establish a preliminary understanding of the underlying mechanisms related to rTMS modulation of synaptic repair in TBI we will also look at Brain Derived Neurotrophic Factor (BDNF) plasma samples in our population.

#### B. Secondary Objectives

1. To evaluate the durability of benefit of rTMS in treatment of executive function deficits (patients receiving rTMS are more likely to show significant improvement at 6 months post treatment than those receiving sham).

2. To evaluate post treatment the impact of rTMS treatment on everyday functioning as defined by the Quality of Life (QOL) scale, a frequently used clinical measure.

3. To evaluate other moderators of response to rTMS treatment such as age, time since injury and severity of PTSD (assessed by PCL-checklist score) as well as depression, sleep substance abuse, fatigue or any combinations of these factors.

4. To evaluate resting state functional MRI (fMRI) as a biological marker of response to rTMS treatment.

5. To evaluate underlying biological mechanisms involving BDNF in synaptic repair and/or change in network connectivity resulting from rTMS treatment.

6. To evaluate improvement in headaches and pain reporting following rTMS treatment using responses on the assessment HIT-6 (HIT-6 has been included with the original protocol on Section 16)

- c) **Explain why human subjects must be used for this project. (i.e. purpose of study is to test efficacy of investigational device in individuals with specific condition; purpose of study is to examine specific**

**Title :** Repetitive Transcranial Magnetic Stimulation to Improve Cognitive Function in TBI  
**Approval Period:** 12/11/2018 - 02/13/2019

**behavioral traits in humans in classroom or other environment)**

The purpose of this project is to study and make recommendations regarding treatment of executive dysfunction in humans.

**2. Study Procedures**

- a) **Please SUMMARIZE the research procedures, screening through closeout, which the human subject will undergo. Refer to sections in the protocol attached in section 16, BUT do not copy the clinical protocol. Be clear on what is to be done for research and what is part of standard of care.**

List of Procedures for the rTMS protocol:

Screening Measures:

- Telephone screening call: 1 hr
- Consenting and on-site screening: approx. 6 hrs
- Physical exam, medical history
- Medication review
- Interviews, self-report questionnaires  
Clinical TBI Evaluation
- Blood (60 cc), urine, and breath tests
- Determination of TMS motor threshold (markings on the cap will be marked with "MT" for motor threshold and "Tx" for treatment site.
- Eligibility determination
- Randomization to active or sham treatment

Baseline measures: approx. 8 hrs

- Interviews, self-report questionnaires, tasks (pain, fatigue, sleep, malingering, depression, PTSD, TBI, suicide, cognition);
- Cognitive testing (including main outcome measure for executive function) and webneuro computerized testing
- Neuroimaging: Diffusion Tensor Imaging (DTI), functional MRI (fMRI); structural MRI
- If indicated, and prior to MRI scan, an MRI X-ray screen will be performed if there is suspicion that participant may have metal in their body
- Pure Tone Audiometry

Intervention Measures:

- rTMS or sham treatment: up to 3 treatments a day for up to 5 days/week, 2-6 weeks = 20 sessions. Each session lasting 30-60 minutes in length. Depending on schedule, and at the physician's discretion, up to three rTMS sessions can be scheduled per day with a one hour interval between sessions, shortening treatment duration to 1.5 weeks.
- TMS motor threshold determination prior to the first treatment and every 5th day of treatment thereafter (at least weekly).
- Random breathalyzer and urine tests will be administered during the intervention phase to screen for drug and alcohol use; depending on results, participant may not be allowed to receive

**Title :** Repetitive Transcranial Magnetic Stimulation to Improve Cognitive Function in TBI  
**Approval Period:** 12/11/2018 - 02/13/2019

additional rTMS treatment for safety reasons

- Blood samples (60 cc) will be taken every 10 rTMS

treatment

for processing of BDNF from blood plasma.

- Headache and Pain self report will be recorded before and after every treatment session.

Follow-up (post treatment and 6 months): approx. 8.5 hrs

- Interviews, Self-Report Questionnaires (same as above);
- Pure Tone Audiometry;
- Cognitive testing including executive function main

outcome measure and webneuro computerized testing

• Neuroimaging: Diffusion Tensor Imaging (DTI), Functional MRI (fMRI), structural MRI

• Blood samples (60 cc) will be taken for processing of BDNF from blood plasma.

- b) Explain how the above research procedures are the least risky that can be performed consistent with sound research design.**

The study design involves minimal risk to participants. This research project is a placebo control study design.

- c) State if deception will be used. If so, provide the rationale and describe debriefing procedures. Since you will not be fully informing the participant in your consent process and form, complete an alteration of consent (in section 13). Submit a debriefing script (in section 16).**

Deception will not be used.

- d) State if audio or video recording will occur. Describe what will become of the recording after use, e.g., shown at scientific meetings, erased. Describe the final disposition of the recordings.**

None will occur.

- e) Describe alternative procedures or courses of treatment, if any, that might be advantageous to the participant. Describe potential risks and benefits associated with these. Any standard treatment that is being withheld must be disclosed in the consent process and form. (i.e. standard-of-care drug, different interventional procedure, no procedure or treatment, palliative care, other research studies).**

There are many alternative procedures/courses of improving executive function including cognitive training, weight loss, exercise, etc although their clinical feasibility can be questioned. No standard treatments for improving executive function are being withheld from potential participants in this study.

- f) Will it be possible to continue the more (most) appropriate therapy for the participant(s) after the conclusion of the study?**

If rTMS is found to be effective for improving cognitive function, it may be possible to have patients return for booster sessions.

- g) Study Endpoint. What are the guidelines or end points by which you can evaluate the different treatments (i.e. study drug, device, procedure) during the study? If one proves to be clearly more effective than another (or others) during the course of a study, will the study be terminated before the projected total participant population has been enrolled? When will the study end if no important differences are detected?**

Study Personnel will generate tabulations of Serious Adverse Events

**Title :** Repetitive Transcranial Magnetic Stimulation to Improve Cognitive Function in TBI  
**Approval Period:** 12/11/2018 - 02/13/2019

(SAEs) and Unanticipated Adverse Device Effects (UADEs) and present a summary of these to the Data Monitoring Committee (DMC) on a schedule set by the DMC. The DMC will also determine when they should be unblinded to treatment assignment for the reviewing of adverse event data. The DMC will advise the PI concerning whether the study should continue or be stopped for safety reasons.

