**d) Sufficient time.**

**Explain whether you will have sufficient time to conduct and complete the research. Include how much time is required.**

This project is expected to last for 2 years. The duration of the study will be two years, with 18 month enrollment period, and the last six months will be strictly for follow-up. 20 participants will be recruited in the first year and 20 will be recruited in the second year. Each participant will be in the trial for a total of approximately 28 weeks (1-2 weeks screening, 2 weeks acute treatment phase (depending on scheduling constraints) and a follow-up visit at 26 weeks post-treatment. The last 6-8 months of the study will also be spent analyzing data and writing up results.

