**Primary Hypothesis:**

Veterans with mild to moderate TBI receiving active rTMS treatment will show improvement of > 1 SD on performance between baseline and post-treatment on any one of the following: the Trail Making Test part B, D-KEFS Verbal Fluency and/or D-KEFS Color-Word Interference Test) than Veterans receiving sham rTMS.

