Patients who are screened over the telephone for possible eligibility for the study will be listed on the Patient Screening Log. Note: we will make all our efforts to screen patients for both rTMS and MRI exclusions but as our primary aim is to test rTMS for use in TBI population, we will enroll participants in the study who are ineligible to be in the MRI scanner but eligible for rTMS treatment. After the patient signs the Informed Consent Form, the on-site screening procedures and assessments can be initiated.

Data will be collected on paper forms and questionnaires, and entered into encrypted, password-protected databases located on physically secure VA servers behind a firewall. All types of data collected will be de-identified according to the VHA Privacy Handbook 1200.12. Each subject will be assigned a subject ID (SUBID). The SUBID codebook will be maintained by the PI, and will be available to appropriate members of the research team but kept in a locked file cabinet or in an encrypted, password-protected file on a physically secure, password protected computer at VAPA.

All research personnel involved in this study will have successfully completed all applicable VA, and Stanford training. All subject-level identifiable data will be treated as Protected Health Information (PHI) unless that data does NOT contain any of the data elements that HIPAA considers protected. No sensitive data or PHI will be stored on any device other than the secure server. Paper forms will be stored in locked file cabinets in locked offices.

Data from the rTMS study will be entered into a designed ACCESS database and maintained on a VA server located at VAPA, password protected, encrypted and no PHI will be present.

**j) Describe how you will be cognizant of other protocols in which participants might be enrolled. Please explain if participants will be enrolled in more than one study.**

We will ask the potential subject if they are participating in any other protocols. They will be instructed not to participate in any other protocols during their involvement with our study without first getting prior authorization from both our research team and that of the other study. Overlapping participation will be handled on a case-by-case basis.

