**l) Costs. Please explain any costs that will be charged to the participant.**

**Title :** Repetitive Transcranial Magnetic Stimulation to Improve Cognitive Function in TBI  
**Approval Period:** 12/11/2018 - 02/13/2019

There are no costs to participants other than time and inconvenience.

**m) Estimate the probable duration of the entire study. Also estimate the total time per participant for: (i) screening of participant; (ii) active participation in study; (iii) analysis of participant data.**

Duration of the study: 2 years

Total time per participant for all screening: 7-8 hours.

For active participation in the study -

- Baseline: approximately 8 hours on-site with MRI, labs, clinical exams
- Intervention: approx. 30-60 minutes/session, 20 sessions over 2 -6 weeks, depending on scheduling
- Follow-up: one follow-up visits over 6 months, each visit lasting approx. 8.5 hrs

Analysis of participant data immediately post treatment and at 6 month follow-up

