**locked environment.**

**By checking this box, You affirm the aforementioned. Y**

Data will be collected on paper forms and questionnaires, and entered into encrypted, password-protected databases located on physically secure VA servers behind a firewall. All types of data collected will be de-identified according to the VHA Privacy Handbook 1200.12. Each subject will be assigned a subject ID (SUBID). The SUBID will be maintained by the PI, and will be available to appropriate members of the research team but kept in a locked file cabinet or in an encrypted, password-protected file on a physically secure, password protected computer at VA Palo Alto. MRI images collected at the VA Palo Alto will be kept on secure VA server and will adhere to all the OI&T and privacy rules. If MRI is to be transferred to Stanford for analysis, it will be done via a HIPAA agreement and consent of the participant. The PI together with the Study coordinator (SC) are responsible for maintaining accurate, complete and up-to-date records for each participant. The PI is also responsible for maintaining any source documentation related to the study, including any films, tracings, computer discs or tapes.

Every attempt will be made to randomize a participant so that he/she will receive his/her first rTMS treatment as soon as possible after randomization. Nonsequential treatment numbers will be assigned to help ensure the confidentiality of veteran participants (see Human Subjects also).

All personnel involved in this study will have successfully completed all applicable VA, and Stanford training. All subject-level identifiable data will be treated as Protected Health Information (PHI) unless that data does NOT contain any of the data elements that HIPAA considers protected. No sensitive data or PHI will be stored on any device other than the secure server. Paper forms will be stored in locked file cabinets in locked offices.

Data from the rTMS study will be on a VA server located at VA Palo Alto, password protected, encrypted and no PHI will be present. Specifically, data in the ACCESS database will be on the secure VA server.

- d) Describe how data or specimens will be labeled (e.g. name, medical record number, study number, linked coding system) or de-identified. If you are de-identifying data or specimens, who will be responsible for the de-identification? If x-rays or other digital images are used, explain how and by whom the images will be de-identified.**

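### The procedure list in Protocol Section 2(a) puts randomization before the baseline testing that the primary outcome needs

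*Protocol*

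**What the plan says.** Section 2(a) of the protocol sorts the procedures into four blocks: screening, baseline, intervention and follow-up. The last two screening items are the eligibility decision and "Randomization to active or sham treatment". The baseline block comes next, at about 8 hours. It contains "Cognitive testing (including main outcome measure for executive function) and webneuro computerized testing", the neuroimaging and, where metal is suspected, an X-ray before the scan. The screening block lists no test of the primary outcome.

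The Primary Hypothesis in Section 1 is stated as "improvement of > 1 SD on performance between baseline and post-treatment on any one of the following", followed by three executive function tests.

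Four other places bear on the order:
- Section 8(m) gives "Total time per participant for all screening: 7-8 hours" and then, under active participation, "Baseline: approximately 8 hours on-site with MRI, labs, clinical exams".
- Section 11(c) says that every attempt will be made so that the participant receives "his/her first rTMS treatment as soon as possible after randomization".
- Resources (d) describes a participant's time as "1-2 weeks screening, 2 weeks acute treatment phase" and then a follow-up visit, with no separate place for baseline.
- Section 8(i) says "we will enroll participants in the study who are ineligible to be in the MRI scanner but eligible for rTMS treatment".

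**The concern.** A change score needs a baseline value. If allocation comes first and the baseline tests follow, there is an interval in which a person already counts as randomized but has not been measured. Someone who leaves in that interval, or turns out to be ineligible, stays in the randomized set, and the outcome in the Primary Hypothesis can never be computed for them. With the tests first, the same person would be lost before randomization, and every randomized participant would have a baseline. The loss is avoidable because it comes only from the order of the steps. An analysis plan can say how to treat such participants, but it cannot recover the missing value.

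**Working it through.** The protocol states no figure to reproduce. The check compares the sections and adds a little arithmetic.

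1. **Order in Section 2(a).** The blocks run screening, baseline, intervention, follow-up, which is their natural order in time. Randomization closes the first block. The executive function outcome test first appears in the second.

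2. **Is there a fallback score from screening?** No outcome test is listed under screening. Section 8(f) records that the Trail Making Test B entry criterion was removed, so the listed procedures do not guarantee a screening score on that test either.

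3. **Does another section reverse the order?** None does so expressly. Resources (d) does not mention baseline and settles nothing. Section 11(c) points towards a short gap between randomization and first treatment, which is hard to square with about 8 hours of testing and imaging in between.

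4. **Hours.** Section 2(a) gives 1 h by telephone and about 6 h on site: 1 + 6 = 7 h. This agrees with the 7-8 h for all screening in Section 8(m). With the baseline block included the total would be 7 + 8 = 15 h. Baseline is therefore counted outside screening. This is weak support only, for the reason given under the objection.

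5. **Who could fall into the interval?**
   - A participant who withdraws after allocation.
   - A participant found ineligible at the X-ray check. Metal in the brain is an exclusion in Section 8(h), and Section 4(c) says that the check may be a skull film. This route is narrow. Metal is first asked about in the telephone screen, Section 4(c) expects few such films, and Section 8(i) keeps people who cannot be scanned but can have rTMS.

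6. **Size of one case.** The protocol gives 40 participants in Sections 8(g) and 9(d), and 100 in Section 8(a). If everyone in the target is randomized, one participant without a baseline is 1/40 = 2.5% or 1/100 = 1%. With baseline completed before randomization, the number randomized without a baseline is 0 by construction.

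**The case against.** The strongest reply is that Section 2(a) does not fix an order at all. The form asks for a summary and refers to attachments that are not at hand. Within blocks the items are plainly not chronological: the X-ray that precedes the scan is listed after the imaging, and the motor threshold measured before the first treatment is listed after the treatments. Randomization may have been placed beside eligibility for administrative convenience, and Section 11(c) suggests that the pre-treatment work was meant to be finished first. This stands in part. It lowers confidence that participants would really be allocated before testing. It does not supply a statement that baseline comes first, and the blocks themselves do run in time order.

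The hours argument is also open to attack. Section 8(m) puts labs and clinical exams with baseline, while Section 2(a) puts the physical exam, blood and urine under screening. The two sections draw the boundary differently, and hours per block do not date randomization. That objection stands, so the conclusion does not rest on the hours.

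Three stronger readings are tempting, and the documents do not support them:
- A reader might infer that the baseline structural MRI would reveal excluded lesions after allocation. No section says that the scan is read for eligibility, and Section 8(i) enrolls people who cannot be scanned.
- A reader might infer a loss of power. A person who leaves before baseline would usually have no post-treatment score either, so the number who can be scored is the same in either order.
- A reader might infer that baseline scores would be biased by allocation. Nothing says that participants or testers learn the assignment before testing, and Section 3 describes a sham meant to be harder to tell from active treatment.

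How the analysis handles randomized participants without a baseline belongs to the statistical analysis plan and is not criticized here.

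**Conclusion.** The point holds as a minor one. As listed, randomization precedes the baseline testing that the primary outcome depends on, no section says otherwise, and the list fits poorly with Section 11(c). Followed literally, it allows participants into the randomized set for whom the change from baseline cannot be computed.

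The number affected cannot be estimated, because the protocol gives no loss rate for this interval. Each case is 2.5% of 40 or 1% of 100, assuming that the whole target is randomized. The conclusion assumes that the order of the blocks reflects the order of conduct, which a summary list makes likely but not certain. What is at stake is whether the randomized set contains people who cannot be scored. The number scored, the precision and the baseline scores themselves are not in question.

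**What to change.** In Section 2(a), move the randomization item out of the screening block. List it after completion of the baseline measures and immediately before the first session, so that Sections 2(a) and 11(c) agree. If baseline testing is already meant to come first, the same edit records it.

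The cost is moving one line. The listed procedures are unchanged, and no visit, staff or test is added.

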### 3. Background

#### a) Describe past experimental and/or clinical findings leading to the formulation of the study.

Overview of rTMS in Cognitive Dysfunction in mild and Moderate TBI  
 Repetitive TMS is a method of delivering therapeutic, non-invasive brain stimulation. While not yet utilized in TBI research on a large scale, rTMS is well suited for this pilot project given the clinical and research expertise in rTMS trials for various other common Veteran complaints (e.g., team of 5 MD's, 1 RN, 3 clinical neuropsychologists and 2 neuroimaging researchers in the VA). rTMS is currently being used at the VA Palo Alto and Stanford University in the treatment of: pain (VA Rehabilitation grant funded: PI: [name] & Co-I/Co-Protocol Director: [name]), depression (VA Co-op studies funded, PI: [name]; Co-op studies funded, PI: [name]), and PTSD (NIH funded project: [name]). At present it is an FDA-approved for treatment for major depression (Oreardon et al., 2007; George et al., 2010; [name], current consultant). A recent VA study reported improvements in PTSD and related symptoms in Veterans with PTSD who received rTMS (Watts et al., 2012). Also of relevance in our TBI Veterans, a major industry trial of rTMS in Treatment Refractory Major Depression (TRMD) has been completed. This randomized controlled trial involved 301 medication-free patients with TRMD and excluded patients dual-diagnosed with co-morbid substance abuse (past year) or PTSD. Response and remission rates were significantly better in rTMS than in controls at the end of 6 weeks treatment, but results were smaller and not

---

**Title :** Repetitive Transcranial Magnetic Stimulation to Improve Cognitive Function in TBI  
**Approval Period:** 12/11/2018 - 02/13/2019

---

significantly better after 4 weeks treatment. Because the 4 week outcome was the a priori defined primary end point, the FDA Advisory panel reviewing this study did not accept this result as adequate support of this new indication for rTMS. However, the most recent data concerning the 12 month durability of a TMS antidepressant effect are quite good, with over 90% retention of remission 12 months later in a treatment resistant group (Demitrack, 2013). This compares to a 50% relapse rate in similar populations who are treated with ECT, or even worse outcomes in patients treated with medications (STAR\*D). We are now rediscovering how exercise, practice, and stimulation can cause plastic changes in the brain (Colcombe et al, 2006). In sum, the only way to discover whether there are acute or more durable effects with rTMS treatment for TBI is to do the proposed study.)

(Rationale for rTMS use in EF improvement: Repetitive TMS treatment can induce neuronal long-term potentiation (Wang et al 2011) involving brain-derived neurotrophic factor (BDNF) resulting in synaptic repair (Cheeran et al., 2008; Lu et al., 2013). Pape et al (2006) reviewed the evidence for rTMS as a possible intervention for TBI-induced cognitive dysfunction in patients with Parkinson's disease and strokes. So far, improvements after rTMS treatments (stimulation site: DLPFC in neurobehavioral outcomes (Pape et al., 2009) and executive function (Pachalska et al., 2011) have only been reported in severe TBI patients. Case studies (Bonni et al., 2013) have found rTMS to lead to improved cognitive functioning in patients with TBI. A recent review of rTMS studies across various mental illnesses strongly suggests its use in TBI to promote recovery and minimize disabilities (Demirtas-Tatlided et al., 2012). Stimulation of the left dorsolateral prefrontal cortex (DLPFC) has led to improvements in major depressive disorder. This brain area has also been shown to be involved in executive

**Title :** Repetitive Transcranial Magnetic Stimulation to Improve Cognitive Function in TBI  
**Approval Period:** 12/11/2018 - 02/13/2019

functioning (Yochim et al., 2007), and we thus hypothesize that stimulation of this area will lead to concomitant improvement in executive functioning).

The proposed pilot study is an advance and necessary for the VA because: 1) It will incorporate dual-diagnosis TBI (mild and moderate) patients including patients with PTSD. These dual-diagnosis patients are usually excluded from industry and National Institute of Health trials and as such the proposed study is unique in that it will address the patient that providers encounter in the VA system specifically. 2) It will focus on improvements in cognitive dysfunction - a major complaint for many Veterans who may not seek medical care and which will impact their cognitive health and independence as they grow older. 3) Furthermore, unlike industry trials, the proposed study will use a sham rTMS procedure that will be more difficult to distinguish from the actual rTMS.

